2.2.3 Dosing Rationale

There are no pre-clinical or clinical data for treatment of FI with FMT product to inform optimal dose. Thus, we have relied on the standard dosage used in other disease states. There are extensive observational studies and several randomized trials that suggest an FMT dose derived from 30-100g of human stool is effective to treat other conditions including Irritable Bowel Disorder and recurrent CDI (Johnsen Lancet 2018; Halkjaer Gut 2018; van Nood NEJM 2013; Youngster JAMA 2014; Kelly CR 2016).

The dose of the PMT investigational product to be employed in this study is based on the use of FMT in prior human studies (See Table 1). A single dose of up to 40g of donated stool, prior to processing into the final form, has been shown to be efficacious in these studies. The PMT products produced from these 40g stool mass contain a range of $1 \times 10^8 - 1 \times 10^{12}$ anaerobic bacterial CFUs. Given the lack of data for women with FI, we will use the dose that has previously been shown to be efficacious in recurrent CDI.

Table 1: FMT dosing and associated risks.

Authors	Publication Year	Population	Study Design	FMT Dose (g stool)	FMT Formulation	FMT Administration	Risks
Hamilton et al	2012	R-CDI	single-group trial	50g stool	250mL suspension	colonoscopy	diarrhea, flatulence
van Nood et al	2013	R-CDI	randomized trial	(not reported)	500mL suspension	duodenal tube	diarrhea, cramping, belching
Youngster et al JAMA	2014	R-CDI	single-group trial	48g stool	30 capsules	oral	cramping, bloating
Kelly et al	2016	R-CDI	randomized trial	64g stool	500mL suspension	colonoscopy	chills, abdominal pain, bloating, nausea, flatulence
Kao et al	2017	R-CDI	randomized trial	80-100g stool	40 capsules or 180mL suspension	oral or colonoscopy	nausea, vomiting, fever, abdominal discomfort
Weingarden et al	2013	R-CDI	case series	50g stool	250mL suspension	colonoscopy	(not reported)
Agrawal et al	2015	R-CDI	case series	~30-60g stool	150-500mL suspension	upper endoscopy, lower endoscopy, enema	diarrhea, constipation, abdominal pain, ileus
Aroniadis et al	2015	R-CDI	case series	(not reported)	suspension	upper endoscopy, lower endoscopy, enema, colonoscopy	diarrhea, abdominal pain
Fischer et al	2015	R-CDI	case series	50-100g stool	300mL suspension	sigmoidoscopy or colonoscopy	treatment failure and death
Fischer et al	2017	R-CDI	case series	50-100g stool	300mL suspension	sigmoidoscopy or colonoscopy	treatment failure and death

2.3 Risk/Benefit Assessment

2.3.1 Known Potential Risks

The main risks of this study are related to administration of the investigational product. The most severe possible risks include allergic reaction, donor-derived infection, aspiration, and death. Other risks include nausea, vomiting, abdominal pain, diarrhea, flatulence, and fever.

As noted above, potential risks of the FMT treatment for FI includes gastrointestinal symptoms (including fever, aspiration, belching, bloating, nausea or vomiting, gastroesophageal reflux, abdominal cramps, abdominal pain, diarrhea, constipation). This is the first attempt to administer FMT for FI in women, however the risks are not expected to be significantly different from that reported in the literature.

Theoretical long-term risks may include: changes in metabolism, weight changes, development of autoimmune conditions.

Other risks include loss of privacy or confidentiality, as a result of study staff interacting with subjects.

These risks will be discussed with subjects during the informed consent process. The eligibility criteria will help mitigate these risks (e.g., excluding subjects with neutropenia or bowel perforation, and not permitting subjects at risk for aspiration to receive investigational product via upper gastrointestinal delivery). To minimize the risk of privacy and confidentiality loss, the minimum number of required study staff will interact with subjects, and all collected data will be protected as above.

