1 STUDY SUMMARY

1.1 Synopsis Title: Fecal Microbial Transplantation (FMT) For the Treatment of Fecal Incontinence in Women FMT for FI **Short Title:** Open label pilot study assessing FMT to treat fecal incontinence in Study women > 50 years of age. **Description: Objectives:** The primary objective is to determine if fecal microbial transplantation leads to clinical improvement in fecal incontinence. Change in the St. Mark's Vaizey score, a measure of fecal incontinence Primary severity, 4 weeks after FMT. **Endpoint:** Secondary Determine whether the effectiveness of microbial engraftment following **Endpoints:** fecal microbial transplantation is associated with the degree of clinical improvement. Determine whether the baseline microbiota configuration affects engraftment in fecal microbial transplantation for fecal incontinence. Our working hypothesis is that the transplant will be more effective in baseline samples with lower microbial diversity. 15 evaluable women, > 50 years of age, who have been diagnosed with Study **Population:** fecal incontinence and have failed standard treatment. 1/2Phase: **Description of** Penn Medicine - University of Pennsylvania Health System Sites/Facilities Participants will be enrolled form the Urogynecology clinics at the Enrolling University of Pennsylvania. **Participants: Description of** Participants will undergo fecal microbial transplantation (FMT) using the Penn Microbiome Therapy – 002 (PMT-002): no more than 152 mL Study **Intervention:** suspension for intragastric or intraduodenal administration from 40g human stool, comprising $1 \times 10^8 - 1 \times 10^{12}$ anaerobic bacterial CFUs/dose. **Study Duration:** 24 months **Participant** Approximately 8 months **Duration:**

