4.3 Justification for Dose and Route of Administration

There are several routes available for the administration of FMT. For this proof of concept study, FMT will be performed via duodenal infusion of donor stool rather than FMT capsules as a single study showed lower efficacy of capsules in women with irritable bowel syndrome (IBS). Our rationale for choosing FMT via duodenal infusion over colonoscopy is as follows: 1) Duodenal infusion FMT is an office-based procedure performed in an awake patient as compared to FMT via colonoscopy in the operating room under sedation, with a risk of bowel perforation and with much higher associated costs. 2) Duodenal infusion FMT is well tolerated by older adults (van Nood, NEJM, 2013; Pinn, Am J Gastro, 2014; Vrieze, Gastroenterol, 2012). 3) Several studies show that FMT via colonoscopy or duodenal infusion have equivalent efficacy (Ramai, Ann Gastro 2019). As described above, the dosing regimen for FMT in recurrent *Clostridium dificile* (R-CDI) will be used as there have been no studies on optimal dosing of PMT-002 in women with FI.

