5.2 Exclusion Criteria

- Known food allergy that could lead to anaphylaxis
- Contraindications to nasogastric tube placement including:
 - Recent midface trauma
 - History of basilar skull fracture
 - Recent ENT surgery
 - Known coagulation abnormalities
 - Esophageal varices and/or esophageal strictures
- Untreated prolapse beyond the hymen
- History of Inflammatory Bowel Disease (does not include IBS)
- Unrepaired rectovaginal fistula/chronic 4th degree laceration
- Full thickness rectal prolapse
- History of congenital anorectal malformation
- History of bowel resection surgery for any indication
- Minor anal procedures within 6 months for treatment of accidental bowel leakage (ABL) (injection of bulking agent or radiofrequency energy) or ligation of hemorrhoids
- Prior pelvic or abdominal radiation
- Diagnosis of cancer of the descending colon or anus

```
FMT for FI
IRB#: 834196
```

- Clinically significant neurological disorders known to affect anal incontinence
- Chronic antibiotic use (>1 month continuous antibiotic)
- Pregnant or planning to become pregnant during the study duration 1 year
 - N/A if participant is not of childbearing potential
- Childbirth within the last 3 months
- Unwilling to use an acceptable form of birth control method if participant is of childbearing potential
 - N/A if participant is of not of childbearing potential
- Participation in another intervention trail impacting bowel function
- Inability to provide informed consent, complete questionnaires independently or to attend intervention sessions
- History of hepatitis C / HIV infection or other immunocompromised condition
- History of bowel resection surgery or pelvic irradiation
- Unable to speak, read, or write in English at a basic level
- In the opinion of the investigator not suitable for participation in the trial

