6.1.2 Dosing and Administration

A single dose of PMT-002 will be administered via a gastroduodenal tube over 10 to 90 minutes (target 30 minutes). In brief, nasogastric duodenal tube will be placed by a physician and its location will be checked by X-Ray. Once placement is confirmed, the PMT-002 product will be delivered via the NGT using a syringe attached to the end of the tube. Once the product has been delivered, the NGT will be removed. The patient will be observed for 1 hour in the office for potential adverse events.

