6.2.2 Formulation, Appearance, Packaging, and Labeling

PMT-002 is composed of donor stool, glycerol, and saline contained in cryobags and labelled (according to FDA regulations 21CFR312.6) for upper GI use. These cryobags will also be labeled with a unique color label to facilitate identification as a PMT-002 drug product.

The potency of each PMT-002 is $1 \times 10^8 - 10^{12}$ CFU/dose (1 dose per cryobag), based on Quantitative Anaerobic Culture from Fecal Filtrate. The appearance of the PMT-002 is frozen aqueous solution within the product container is properly labeled, free of defects. Prior to release of the drug product, all serological, stool and multi-drug resistant organism (MDRO) testing will be confirmed to be negative.

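### Section 2.3.1 relies on the eligibility criteria to keep women at risk of aspiration from upper-GI delivery, but no criterion in 5.1 or 5.2 names that risk and an upper-GI tube is the only route

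*Combined protocol and SAP*

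**What the plan says.** Section 2.3.1 (Known Potential Risks) ranks the hazards of giving the product: "The most severe possible risks include allergic reaction, donor-derived infection, aspiration, and death". It then says that the eligibility criteria will help to mitigate the risks and gives three examples: excluding neutropenia, excluding bowel perforation, and "not permitting subjects at risk for aspiration to receive investigational product via upper gastrointestinal delivery".

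The route is described in several places, each time as upper GI:

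- Synopsis (1.1): "suspension for intragastric or intraduodenal administration from 40g human stool", with a volume of at most 152 mL.
- Section 4.3: "FMT will be performed via duodenal infusion of donor stool rather than FMT capsules". The same section also explains why colonoscopy was not chosen.
- Section 6.1.2: "A single dose of PMT-002 will be administered via a gastroduodenal tube over 10 to 90 minutes".
- Section 6.2.2: the product is "contained in cryobags and labelled (according to FDA regulations 21CFR312.6) for upper GI use".

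The nearest criteria in 5.2 are the item headed "Contraindications to nasogastric tube placement including", which is followed by five named conditions, and the closing item, "In the opinion of the investigator not suitable for participation in the trial".

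**The concern.** A risk section that credits the eligibility criteria with a control should be traceable to those criteria. Section 5.5 has potential eligibility confirmed clinically against the inclusion and exclusion criteria, so these are what screeners work from. If aspiration risk is not named there, whether a woman with, say, dysphagia or gastroparesis is turned away depends on someone thinking of it.

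Participant safety is at stake. The protocol treats aspiration as one of the gravest hazards, and 2.2.2 and 8.3.3.3 list it among events that may be common after dosing. Section 5.1 sets no upper age limit and provides for women over 75. This is the first use of FMT for this indication, and 5.3 says that the product cannot be retrieved once it has been given.

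**Working it through.** No formula applies and the plan gives no figure to reproduce. The check compares the statement in 2.3.1 with the criteria, the route and the other controls.

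**1. Where aspiration appears.** Count of the word in the supplied text:

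- 2.2.2: 1
- 2.3.1: 3
- 8.1.2.1: 2
- 8.3.3.3: 3
- 5.1 and 5.2: 0

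Total: 1 + 3 + 2 + 3 = 9. One of the nine, the mitigation example in 2.3.1, concerns who may receive the product. The other 9 − 1 = 8 list aspiration as a risk, or as an event to watch for or ask about after dosing.

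**2. Whether a criterion covers it in other words.** Section 5.1 deals with age and the definition of incontinence, baseline St. Mark's score, constipating medication, colon cancer screening and consent. Neither 5.1 nor 5.2 mentions dysphagia, swallowing, reflux, gastric emptying or airway protection. Four items in 5.2 give some cover:

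- *Nasogastric-tube contraindications.* The list is open-ended, and exclusion is mandatory once a physician judges that a contraindication applies. The five named examples (midface trauma, basilar skull fracture, ENT surgery, coagulation abnormality, esophageal varices or strictures) are hazards of passing a tube. Stricture comes nearest to aspiration risk.
- *Investigator opinion.* General and discretionary.
- *Neurological disorders.* Limited to those that affect anal continence. It may remove some women with impaired swallowing, but only incidentally.
- *Inability to consent or complete questionnaires independently.* Removes some women with impaired cognition, but not a cognitively intact woman with dysphagia or gastroparesis.

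**3. Whether an at-risk woman could be dosed another way.** She could not. The synopsis, 4.3, 6.1.2, 6.2.2 and 8.1.2 leave an upper-GI tube as the only route. Not permitting upper-GI delivery therefore means not entering the trial, and that exclusion is not written explicitly.

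**4. Whether another control does the same job.**

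- Before and during dosing: a physician places the tube and its position is confirmed by X-ray (6.1.2, 8.1.2). Section 6.2.1 allows for administration being stopped before it is complete. These steps reduce risk, but X-ray checks the tube and not the woman's own susceptibility.
- After dosing: observation at 30 and 60 minutes (8.1.2.1), expedited reporting of gastrointestinal events of Grade 3 or higher (8.3.4) and the pause rules (8.3.8). The pause rules protect women still to be dosed, but only after an event in someone else.

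None of these selects out a woman at raised aspiration risk.

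**5. The other two examples in the 2.3.1 sentence.** Neutropenia is reasonably covered by the exclusion of immunocompromised women. Bowel perforation is not named in 5.1 or 5.2; this is a minor item.

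**The case against.** The strongest reply is that 2.3.1 promises only that the criteria will help, with illustrative examples, and that 5.2 already contains the means. A physician who regards aspiration risk as a contraindication to the tube must exclude the woman under the existing text, and the investigator-opinion item covers anything left. Section 5.5 calls the eligibility check a clinical confirmation and involves the principal investigator or treating physician. The eligibility checklist (8.1.1) and the manuals of procedures (10.1.6) were not supplied and may already ask about aspiration.

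Much of this stands. A reader might infer that the criteria offer no protection at all, and the documents do not support that: discretionary cover exists and a woman at obvious risk may well be stopped. A reader might also infer that nothing can be done once dosing starts. Section 5.3 speaks of the period after administration, and 6.2.1 allows a dose to be stopped part-way.

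Two further inferences go beyond the text. One is that the wording of 2.3.1 reveals a second delivery route; with a single route it can simply mean exclusion. The other is that the IRB or DSMB has been misled; 5.2 is in the same document, and nothing shows what those bodies believed.

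What the reply does not answer is that a general discretion clause could cover any omission. It gives the screener no prompt for a hazard that the protocol ranks among its most severe and says its criteria address.

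**Conclusion.** The point holds in a limited form. Section 2.3.1 credits the eligibility criteria with a safeguard against aspiration that no criterion in 5.1 or 5.2 explicitly names. With one route, that safeguard can operate only as exclusion from the trial. Present cover is partial or depends on a physician's judgement, so a woman at raised risk could satisfy every named criterion and be dosed.

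In size: no explicit criterion, no alternative route, and all 15 planned women exposed to upper-GI delivery. How many would be at raised risk, and how many of those a physician would miss, cannot be estimated from the documents, and no probability is claimed. The conclusion assumes that 5.1 and 5.2 as supplied are the complete criteria. If the checklist already carries an aspiration item, the practical risk is smaller and what remains is an inconsistency in the protocol text.

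It should be fixed because the control is safety-related and the remedy is cheap. It has no bearing on the endpoint, sample size or analysis, and it is not an argument that the trial is unsafe to run.

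**What to change.** Add one line to 5.2 that excludes women at increased risk of aspiration, for example those with dysphagia, known gastroparesis, prior aspiration or impaired airway protection. These examples are suggestions and do not come from the protocol; the investigators should settle the list. Carry the item into the eligibility checklist used at screening (8.1.1) if it is not already there.

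Reword the sentence in 2.3.1 to say that women at increased risk of aspiration are excluded because PMT-002 is given only by the upper-GI route. Optionally, add an exclusion for current or recent bowel perforation so that all three examples in that sentence can be traced to 5.2.

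The cost is a short amendment: one or two lines in 5.2, one reworded sentence and matching checklist items. The downside is possibly a few more screen failures in a 15-woman study.

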2.3.2 Known Potential Benefits

Currently, it is unknown if benefit will be received from participation. It is hypothesized that symptoms of FI will improve after administration of FMT.

2.3.3 Assessment of Potential Risks and Benefits

Gastrointestinal symptoms have been reported following FMT administration in patients with R-CDI (see Table 1). While FMT has not previously been administered for treatment of fecal incontinence, we anticipate that women recruited for this study will be most similar to subjects with irritable bowel syndrome who received FMT. In this patient population, no serious adverse event has been reported following treatment with FMT in several studies (Johnsen, Lancet, 2018; Halkjaer, Gut, 2018). Given the immense burden of FI on quality of life, the potential benefit of improvement in severity of fecal incontinence symptoms vastly outweighs the risk of transient gastrointestinal symptoms.

3 STUDY OBJECTIVES AND ENDPOINTS

OBJECTIVES	ENDPOINTS
Primary	
Determine if fecal microbial transplantation leads to clinical improvement in refractory fecal incontinence in older women.	Number of subjects that show significant improvement at 4 weeks after FMT, and will be maintained at 12 weeks, relative to baseline using the St. Mark's Vaizey score, a measure of fecal incontinence severity.
Primary Safety	
Determine the safety of FMT administration via naso-gastric tube in older women with FI.	Frequency of adverse events, serious adverse events, and adverse events of special interest (including allergic reaction and gastrointestinal symptoms).
Secondary	
Determine if FMT leads to improved quality of life for subjects.	Number of subjects that have an improved quality of life at 4 and 12 weeks, measured by the FIQL scale.
Determine if the effectiveness of microbial engraftment following fecal microbial transplantation is associated with the degree of clinical improvement.	Concentration of microbiota present at baseline vs. at week 4 and at 12 weeks (optional)in subjects that demonstrate a significant improvement at 4 weeks after FMT, relative to baseline using the St. Mark's Vaizey score.
Tertiary	
Determine whether the baseline microbiota of the subject affects engraftment in fecal microbial transplantation for fecal incontinence.	Concentration of microbiota at baseline vs. concentration of microbiota at 4 weeks and at 12 weeks (optional).

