8.1.4 Visit 2 (4 weeks post treatment)

Subjects will come to the office for a visit 4 weeks (\pm 7 days) after administration of the FMT treatment or be conducted by telemedicine or telephone.

During their first follow-up visit, the subjects will return to the clinical site in person or via mail:

- Second one-week bowel movement (BM) diary
- Temperature and Adverse Events log form
- Stool specimen

During the visit, the following forms will be completed:

- Medication Log
- Adaption Index
- SF-12
- PFDI-20 (Pelvic Floor Disability Index)
- ABLe Questionnaire
- FIQL (Fecal Incontinence quality of life)
- Bristol Stool Index
- St. Mark's Score
- PGSC (Patient Global Symptom Control)

- Global Impression Improvement
- PACSYM
- PFIQ-7
- AE/SAEs

Subjects will be sent home with a final one-week BM diary that they will return during their 12week visit. The diary will include a card for the collection of all solicited adverse events. Subjects will also be sent home with a stool collection kit to be returned at the 12-week visit or be returned by mail if a telemedicine or telephone visit (optional).

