9.2 Primary	
Determine if fecal microbial transplantation leads to clinical improvement in refractory fecal incontinence in older women.	Our working hypothesis is that the St. Mark's Vaizey score, a measure of fecal incontinence severity, will significantly improve at 4 weeks after FMT, and will be maintained at 12 weeks, relative to baseline. A secondary outcome will be quality of life at 4 and 12 weeks.
Primary Safety	
Determine the safety of FMT administration via NG tube in older women with FI.	Our hypothesis is that there will be low occurrence of serious adverse events following administration of FMT via NG tube.
Secondary	
Determine whether the effectiveness of microbial engraftment following fecal microbial transplantation is associated with the degree of clinical improvement.	Our working hypothesis is that more transplanted strains will be present at 4 weeks in subjects with a higher response score.
Tertiary	
Determine whether the baseline microbiota configuration affects engraftment in fecal microbial transplantation for fecal incontinence.	Our working hypothesis is that the transplant will be more effective in baseline samples with lower microbial diversity.

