9.1 Statistical Hypotheses

9.3 Sample Size Determination

Initial open label clinical trials of FMT for irritable bowel syndrome were performed with 10-15 patients. (Holvoet, Gut 2017; Pinn ,Am J Gastro, 2014; Mazzawi, PLoS One, 2018) In the proposed pilot study, we will examine 15 evaluable women with refractory fecal incontinence to gather essential feasibility and outcomes data to conduct a future RCT of FMT. In a prior study of 13 adults with irritable bowel syndrome, significant differences in signals for several bacteria (*Bacteroides, Desulfitispora, Bifidobacteria*) were noted between 8 responders and 5 non-

responders to FMT (response rate 60%). (Mazzawi PLoS One, 2018) If the response rate is near 60% in our pilot study, we will be able to detect a difference in bacterial engraftment of 1.59 standard deviations. Our power will be decreased if the response rate is either very low (<3) or very high (>12). With 15 subjects in a single arm study, the response rate will be determined to within 10% (interquartile range).

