9.4 Statistical Analyses

9.4.1 General Approach

Data on safety outcomes will be summarized using descriptive statistics. Feasibility of conducting a clinical trial of FMT will be calculated by measuring the feasibility of conducting a clinical trial of FMT will be calculated by percentage of screened patients who enroll in the study (Number enrolled / Number screened x 100). Fecal incontinence severity symptom and quality of life (QOL) scores at baseline, 4 and 12 weeks after FMT treatment will be compared using Friedman test (repeated measures ANOVA for non-parametric data) Responder will be defined as 5 point or greater improvement in St. Mark's score from baseline to 4 weeks following FMT.

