9.4.2 Analysis of Stool Samples

Sequence reads from shotgun metagenomic sequencing will be subjected to quality control, taxonomic assignment, gene function analysis, and metagenomic assembly using the Sunbeam metagenomics pipeline, which was co-written by CHOP Microbiome Center researchers.

The FMT inoculum will be sequenced alongside fecal samples collected from subjects before and after the FMT procedure. DNA sequence reads from the inoculum will be assembled into contigs (overlapping DNA segments) using MEGAHIT (Li Bioinformatics, 2015). The metagenomic contig sequences represent segments of bacterial genomes from the microbiota. We will identify protein coding genes in the contig sequences, and use this gene set as unique identifiers for the genomes in the inoculum. Reads from patients before and after FMT will be aligned to the inoculum marker gene sequences. Gene sequences which are present in patients before the transplant will be removed from the set of inoculum marker genes. The percentage of total non-human reads aligning to the inoculum marker gene set will be used as a measure of bacterial engraftment following FMT.

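### The Section 3 engraftment endpoint covers only women who improve, so it cannot show whether engraftment is related to improvement, and Section 9.4 names no analysis that does

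*Combined protocol and SAP*

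**What the plan says.** All references are to the combined protocol and SAP.

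- **Section 1.1 (synopsis).** The association between engraftment and degree of improvement is listed among the secondary endpoints, with no limit to women who improve.
- **Section 3, secondary objective.** The same association is the aim. The endpoint beside it is "Concentration of microbiota present at baseline vs. at week 4", with week 12 optional, in "subjects that demonstrate a significant improvement at 4 weeks after FMT".
- **Section 9.2 (hypotheses table), secondary.** The expectation is that "more transplanted strains will be present at 4 weeks in subjects with a higher response score".
- **Section 9.3.** A prior study of 13 adults with irritable bowel syndrome is cited for differences between 8 responders and 5 non-responders. At a response rate near 60%, "we will be able to detect a difference in bacterial engraftment of 1.59 standard deviations". Power is said to fall with fewer than 3 or more than 12 responders. No test, alpha or power is given.
- **Section 9.4.1.** "Responder will be defined as 5 point or greater improvement in St. Mark's score from baseline to 4 weeks following FMT". The only test named is Friedman's, for symptom and quality-of-life scores over time.
- **Section 9.4.2.** Engraftment is the "percentage of total non-human reads aligning to the inoculum marker gene set", after genes already present in patients before transplant are dropped from that set. No test or model relates it to response.
- **Sections 4.1 and 8.1.4.** All subjects give stool and complete questionnaires. Week 4 collects both a stool specimen and the St. Mark's score.

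**The concern.** An association needs variation in both quantities. The Section 3 endpoint selects on one of them (improvement) and then looks at change over time in the other. A change in microbiota among improvers says that the microbiota changed in those women. It does not say whether it changed less in the women who did not improve, or whether larger changes went with larger improvements.

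This is the only question for which Section 9.3 states a detectable difference, and the pilot is meant to inform a randomised trial. If the table is followed literally, the comparison that was sized cannot be made. If it is not followed, the analyst must choose among the readings in Section 9 after the data exist. A change seen in improvers could also be reported as support for a link that it does not test.

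**Working it through.** **1. The statements side by side**

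| Place | Women | Form of the question | Measure |
|---|---|---|---|
| Section 1.1 | no restriction | association with degree of improvement | engraftment |
| Section 3 endpoint | improvers only | baseline v week 4 | concentration of microbiota |
| Section 9.2 | range of response scores | gradient | transplanted strains |
| Section 9.3 | responders and non-responders | two-group difference | bacterial engraftment |
| Section 9.4.2 | not stated | none | percentage of reads on inoculum marker genes |

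The Section 3 endpoint is the only entry that excludes non-improvers. Sections 9.3 and 9.4.2 share the term bacterial engraftment, so the measure that clearly departs is concentration in Section 3.

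**2. Reproducing 1.59 SD**

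Inputs: 15 women and a 60% response rate (Section 9.3), so 15 × 0.60 = 9 responders and 6 non-responders. Assumed, because the plan does not say: two-sample t test, two-sided 5%.

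- Noncentrality = 1.59 / √(1/9 + 1/6) = 1.59 / 0.527 = 3.017, on 13 df, critical value 2.160.
- Power = 79.6%. The difference detectable with exactly 80% power is 1.60 SD.

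The figure is sound under these assumptions, and it requires the 6 non-responders. With improvers only, no between-group difference can be computed.

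At 12 v 3: noncentrality = 1.59 / √(1/12 + 1/3) = 1.59 / 0.645 = 2.463; power 62.5%; 80% power needs 1.96 SD. This agrees with the plan's remark that extreme response rates cost power.

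**3. Precision of the split**

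95% half-width = 2.160 × √(1/n₁ + 1/n₂).

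- 9 v 6: 2.160 × 0.527 = 1.14 SD.
- 12 v 3: 2.160 × 0.645 = 1.39 SD.

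**4. Why the unnamed analysis matters**

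Sections 9.2 and 9.3 imply two analyses, a gradient and a split. Simulated power with 15 women (40,000 trials per setting, two-sided 5%):

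| Assumed truth | Spearman, all 15 | Responder split, t test |
|---|---|---|
| Bivariate normal, correlation 0.5 | 44% | 31% (9 v 6) |
| Bivariate normal, correlation 0.7 | 81% | 61% (9 v 6) |
| 1.59 SD step at the responder cut | 60% | 80% (9 v 6) |
| 1.59 SD step at the responder cut | 24% | 62% (12 v 3) |

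Neither analysis is always stronger. The correlations are illustrative; the documents give none. As a rough check, the Fisher z approximation with a Spearman variance factor of 1.06 gives a rank correlation detectable with 80% power of tanh(2.80 × √(1.06/12)) = 0.68. That is the Spearman value implied by a bivariate normal correlation of 0.7, since (6/π) × arcsin(0.35) = 0.68.

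**The case against.** The strongest reply is that the intent can be recovered. The synopsis has no restriction, every subject gives stool, Section 9.3 frames responders against non-responders, and Section 9.4.1 defines a responder that Section 9.4 puts to no other use. On that reading, what remains is one badly worded table cell and an unnamed test, for a secondary question in a 15-woman open-label pilot.

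Much of this stands, and it keeps the point below anything that threatens the trial. It does not remove it. The endpoint table still contradicts the rest, the objective and Section 9.2 are graded while Section 9.3 is a split, and Section 9.4 chooses neither.

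A reader might infer more than the documents support:

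- *That the improver-only contrast is bound to be significant.* If every one of 9 improvers gained donor reads, an exact signed-rank test would give 2/2⁹ = 0.004. That joins the Section 3 population to the Section 9.4.2 measure, which Section 3 does not use, and adds a test named nowhere.
- *That the plan intends a correlation within improvers, with poor power.* No section proposes one.
- *That there are three incompatible measures.* The strain wording in Section 9.2 can be read as what Section 9.4.2 puts into operation.
- *That 1.59 SD is wrong.* It reproduces.
- *That Spearman must lead.* The split matches the sizing and is stronger under a step, so the order is the sponsor's choice.

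**Conclusion.** The point holds. As written, the Section 3 endpoint cannot show whether engraftment is associated with the degree of improvement. It conflicts with Section 1.1, Section 9.2 and Section 9.3, its measure departs from Section 9.4.2, and Section 9.4 names no linking analysis. These conclusions come from the text and need no assumption.

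The size rests on assumptions. The 79.6% power assumes a two-sided 5% t test at 9 v 6. The contrasts between Spearman and the split (81% v 61%, 60% v 80%, 24% v 62%) depend on assumed shapes for the relation. They show that the choice should be fixed in advance, not which choice is right.

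The sponsor should correct this before analysis. It affects how the engraftment result can be interpreted, not safety or the primary result.

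**What to change.** **Section 3.** Replace the endpoint with: *week-4 engraftment (Section 9.4.2 measure), with week 12 where available (optional), in relation to improvement in St. Mark's score from baseline to week 4, in all treated women with a week-4 stool sample and score; the number excluded will be reported.*

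**Section 9.4.** Before the data are seen, name one main analysis in all these women and report the other as support:

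- the responder versus non-responder difference in engraftment with 95% CI, which matches the 1.59 SD sizing; or
- a Spearman correlation of engraftment with improvement, with 95% CI, which matches the graded objective.

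**Section 9.3.** Keep 1.59 SD for the 9 v 6 split and state the test, alpha and power behind it. If Spearman leads, add that 15 women give about 81% power at a true correlation of 0.7 and 44% at 0.5 (bivariate normal assumed).

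**Section 9.4.2.** Say whether the marker set, after removal of genes present before transplant, is built separately for each woman. If so, report its size for each woman, since sets of different size may make scores less comparable between women.

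**Cost.** There are no new visits or samples, because week 4 already collects stool and the score. The endpoint's stated measure does change, from concentration to the read percentage. Whichever analysis leads loses power if the truth has the other shape; under a step with 12 v 3, Spearman has about 24% against 62% for the split. Missing week-4 samples also cost power: with 13 women, Spearman has about 73% at a correlation of 0.7.
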